PROTOCOL

Study Title:	Apremilast 30 mg BID combined with Dupilumab for the Treatment of Recalcitrant Moderate-to-Severe Atopic Dermatitis
Study Drug:	Oral Apremilast 30 mg BID
Sponsor :	[name] Tufts Medical Center Department of Dermatology [name] [contact] [contact] E-mail: [contact]
Coordinators :	[name] RN, [name]

Version and Date:

Version June 2, 2021

I. Aim and Hypotheses: The purpose of this study is to determine if apremilast as a combined treatment for atopic dermatitis will provide increased efficacy outcomes in subjects who are currently using the FDA approved therapy of dupilumab but have responded only partially or inadequately to this therapy. Our hypothesis is that adding apremilast will allow patients to go from an inadequate response to dupilumab to an adequate response defined as an Investigator Global Assessment (IGA) of 0 (clear) or 1 (almost clear).

II. Background and rationale:

Background and Rationale:

Dupilumab is FDA approved for atopic dermatitis and has activity against the shared alpha-chain subunit of the IL-4 and IL-13 receptor system. While type 2 inflammation is the predominant problem in atopic dermatitis, Th1 and TH17 inflammation is also part of the pathogenesis. Apremilast alone is unable to sufficiently block the dominant type 2 immune pathway in atopic dermatitis; however, apremilast can decrease multiple cytokine pathways through PDE4 inhibition. Apremilast blocks inflammatory mediators such as TNF- α , IL-12, IL-2 production in AD patients and may improve pruritus by this mechanism.^{1–3} We believe adding apremilast to patients already treated with dupilumab will lead to further improvement in atopic dermatitis and select out the patient population that will most benefit from apremilast. One study using apremilast 30 mg BID versus apremilast 20 mg BID as monotherapy for atopic dermatitis saw a clinical effect after 3 months in the 30 mg BID group only.⁴ We will be using apremilast in combination with dupilumab, and think the results may be synergistic.

Our hypothesis is that the addition of apremilast to dupilumab will allow patients with an inadequate response to dupilumab monotherapy to potentially achieve an Investigators' Global Assessment (IGA) score of 0 (clear) or 1 (almost clear).

2.2) Apremilast (CC-10004):

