 - v. Mean and percentage change from baseline in Eczema Area and Severity Index (EASI) score at week 16

Safety Endpoints:

Safety and tolerability will be evaluated according to the frequency and severity of adverse events and changes in physical examinations or vital signs.

II. Research Plan

A. Overall Study Design:

Open label phase 2 investigational study of efficacy and safety of apremilast 30 mg BID in chronic atopic dermatitis when added to the FDA approved treatment dupilumab for atopic dermatitis that is not providing adequate clinical responses. The study will have 1 phase:

• Open label treatment period apremilast 30 mg BID

Following informed consent, subjects will be screened on the basis of atopic dermatitis severity and inadequate treatment response to current therapies. IGA, BSA, pruritus NRS, EASI, complete physical examination, medical history, and concomitant medications will be reviewed. Eligible subjects will be administered treatment with apremilast 30 mg BID while continuing their prior inadequate atopic dermatitis treatment regimen. During the treatment phase, study drug will be provided in an oral form and will be titrated over 5 days and then taken twice daily thereafter. Subjects return to clinic for reevaluation. Efficacy endpoints will be assessed at weeks 2, 4, 8, 16, and 24. Week 16 is the last week of study drug dispensation. Efficacy and safety indices will be assessed as per the Schedule of Assessments.

Treatment Assignment and Randomization

No randomization will be used, as this is an open label study. There will be no blinding and investigators will have knowledge of the treatment each subject is administered.

All patients seen in the Tufts Dermatology Clinic during the enrollment period who are not currently responding to existing FDA approved atopic dermatitis therapy and thus have not achieved a IGA of 0 or 1 at screening, and meet all other inclusion/exclusion criteria, will be offered participation in the study.

B. Statistical methods:

Sample size: We will screen up to 20 patients to ensure that 16 patients complete the study.

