General statistical Methods: A clinical response to apremilast for the purposes of this study will be defined as an Investigator Global Assessment score of 0 (clear) or 1 (almost clear). The end points of the study will be assessed at Week 16. A period of 16 weeks was chosen, as this was the time frame utilized for primary endpoint reporting in the ESTEEM clinical program.^{6,8} An additional 8 weeks of study drug will be provided to assess enhanced clinical benefit with continued use at 24 weeks. A rate of incompletion and/or drop out of subjects has been factored in to assure great than 16 patients will complete the study.

The analysis will be primarily descriptive. Mean, standard deviation, median, minimum, maximum, and 95% confidence interval for mean will be provided for continuous variables. Changes and percent changes from pre-treatment to on-treatment time points will be calculated for continuous efficacy points. Graphical displays of changes over time may be presented for key outcomes. Counts, percentages, and 95% confidence intervals will be provided for categorical variables. Subgroup analyses, such as gender stratification and stratification based on baseline treatment regimens, will be performed to identify a patient population that achieves the most benefit.

Efficacy analyses will only use data from participants who complete at least 16 weeks of study treatment in order to evaluate the primary endpoint.

Efficacy:

Primary Endpoint

Patients' Investigator's Global Assessment $(IGA)^9$ will be assessed at weeks 2, 4, 8, 16, and 24, with the primary endpoint being the proportion of patients with an IGA of 0 (clear) or 1 (almost clear) at Week 16.

Secondary Endpoints

Secondary endpoints will be assessed according to the scale of the outcome variable of interest. BSA and Eczema Area and Severity Index¹⁰ will be assessed along with IGA at all study visits. For quality of life outcomes, the Dermatology Life Quality Index (DLQI)¹¹ will be used to assess changes from baseline in overall score will be provided. Assessment of outcomes of each protocol-scheduled time point (Weeks 2, 4, 8, 16, and 24) will be performed for each endpoint. Various schemes will be assessed for missing data imputation if needed. The change in the patient's Numerical Rating Scale for Pruritus (NRS) will be assessed.¹²

Background and demographic characteristics:

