drug, or within 30 days of the subject's last dose of study drug, are considered immediately reportable events. Study drug is to be discontinued immediately and the subject instructed to return any unused portion of the study drug to the investigator(s). The pregnancy, suspected pregnancy, or positive pregnancy test must be reported to Amgen Safety immediately facsimile using the Pregnancy Report form provided by Amgen. An authorization form to request the collection of this information from the pregnant partner of a male subject will be submitted to the IRB for review and approval prior to the collection of this information. The study team will request that subject approach their pregnant partner to obtain authorization, and the pregnant partner may contact the study team for more information.

G. Subject Participation

- 1. **Recruitment**: Recruitment will occur through the outpatient dermatology clinic at Tufts Medical Center once IRB approval is obtained. Goals for recruitment in terms of screening treatment regimens include: 16 subjects completing the study. Up to 20 may be screened to allow for screen fails.
 - Dermatologists in the TMC department of dermatology will be informed about the ongoing trial and its key inclusion/exclusion criteria. Dermatologists can inform their patients about the study during the patient's regular scheduled clinic visit. If a patient is interested, research staff will come down to the dermatology clinic to inform the patient further. If the subject chooses to proceed with a screening visit, this will be conducted in a private research room where informed consent will be obtained. Alternatively, the screening visit can be scheduled for a future date. Dermatologists may also tell their patients about this study and provide research staff contact information to the patient
 - The clinical recruitment website will provide online information about the study. Additionally, this trial will be listed on clinicaltrials.gov. Study team contact information will be provided in both of these websites, and interested subjects may call the department for more information. There are no other recruitment materials.
 - These two methods have been effective in the past for our recruitment of other investigator-initiated trials of similar sample sizes.
- 2. Registration: Not applicable.

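### The subgroup analyses aim to identify the patients who benefit most, a conclusion that about 16 completers in one uncontrolled arm cannot support

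*Protocol*

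**What the plan says.** The clause is in the protocol's section on statistical methods, under the general methods, and again in the SAP. It reads "Subgroup analyses, such as gender stratification and stratification based on baseline treatment regimens", and these "will be performed to identify a patient population that achieves the most benefit". The protocol's background and rationale voices a similar hope, that adding apremilast will "select out the patient population that will most benefit from apremilast".

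The design around the clause is small and uncontrolled:

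- **Size.** "We will screen up to 20 patients to ensure that 16 patients complete the study". Efficacy analyses are restricted to subjects who complete at least 16 weeks of treatment.
- **Control.** "No randomization will be used, as this is an open label study". There is a single arm. The section on background characteristics mentions a baseline table comparing treated subjects with controls, but the design contains no control group.
- **Endpoint.** The primary endpoint is the "proportion of patients with an IGA of 0 (clear) or 1 (almost clear) at Week 16". No expected or reference rate is given.
- **Precision.** The analysis is called primarily descriptive. Counts, percentages and 95% confidence intervals are planned for categorical variables, and 95% intervals for means of continuous ones.

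The documents state no comparison between subgroups, minimum subgroup size, multiplicity rule or criterion for declaring that a population has been identified. They do not call the subgroup results exploratory.

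**The concern.** The clause goes beyond summarising results by subgroup, because it assigns the analyses a conclusion. Two separate obstacles stand in the way.

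The first is the missing control. Benefit from apremilast is a difference between outcomes with and without it, and a single arm observes only the former. Entry requires an IGA of 2 or more on dupilumab. A subject who enters at IGA 2 needs a one-step improvement to respond, and a subject who enters at IGA 4 needs three. A subgroup with milder disease could therefore show the higher response rate with no difference in drug effect. More subjects would not cure this.

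The second is size. Splitting about 16 completers leaves cells of eight or fewer in at least one subgroup, and the open factor list leaves the number of splits undefined.

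At stake is a published statement about who should receive the combination. The protocol plans a journal manuscript and, in its risk and benefit section, hopes to inform how apremilast is prescribed.

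**Working it through.** **Inputs from the documents.** Target of 16 completers, at most 20 screened, one arm, a binary primary endpoint, and two named factors (gender and baseline treatment regimen). There is no power calculation to reproduce. The ratio 16/20 = 80% only restates the recruitment target.

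**Assumptions.** Common true response rate of 10% to 50%; splits of 8/8, 10/6 and 12/4; two-sided 0.05 wherever a test is used for scale.

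**1. Chance gaps when the subgroups do not truly differ.** Let X and Y be independent binomial counts in subgroups of size n1 and n2 with the same rate p. Sum P(X = i) × P(Y = j) over all pairs (i, j) that meet the condition.

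Worked case, 8/8 at p = 0.30:

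- P(equal counts) = Σ P(X = i)² = 0.216, so P(some gap) = 1 − 0.216 = 0.784.
- P(counts differ by exactly one subject) = 0.374.
- A gap of 25 points is two subjects of eight, so P(gap ≥ 25 points) = 1 − 0.216 − 0.374 = 0.41.

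Range over p = 10% to 50%, one factor:

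| Split | Some numerical gap | Gap of 25 points or more | Fisher p ≤ 0.05 |
|---|---|---|---|
| 8/8 | 65% to 80% | 19% to 45% | 0% to 2% |
| 10/6 | 81% to 98% | 9% to 36% | 1% to 3% |
| 12/4 | 79% to 89% | 21% to 48% | 1% to 2% |

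For two independent random 8/8 splits of the same 16 subjects (100,000 simulated trials, rates from 10% to 50%), at least one shows some gap in 73% to 93% of trials. At least one shows a gap of 25 points or more in 30% to 68%.

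**2. A true difference of 20% versus 50%, at 8 versus 8.** The same enumeration gives:

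- the truly better subgroup is numerically higher in 85% of trials, the counts tie in 9%, and the worse subgroup is higher in 6%;
- Fisher's exact test reaches p ≤ 0.05 in 12%. For 20% versus 60% it does so in 24%.

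For scale, 80% power for 20% versus 50% by the normal approximation needs

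n = [1.96 × √(2 × 0.35 × 0.65) + 0.842 × √(0.2 × 0.8 + 0.5 × 0.5)]² / 0.30² = 38.5,

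that is 39 per subgroup, or 45 with a continuity correction.

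**3. Precision of an observed result.** Exact (Clopper-Pearson) 95% intervals are 3% to 65% for 2/8 and 16% to 84% for 4/8. For the difference 4/8 − 2/8 = 25 points, Newcombe's method combines the Wilson limits (21.5% to 78.5%, and 7.1% to 59.1%):

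- lower limit: 25 − √(28.5² + 34.1²) = −19 points;
- upper limit: 25 + √(28.5² + 17.9²) = +59 points.

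The planned within-group intervals would show each rate to be imprecise. The interval for the difference, on which any comparison of subgroups depends, is not planned.

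**The case against.** The strongest reply is that the clause carries little weight. The analysis is declared primarily descriptive, and the objectives list no subgroup endpoint. The section on outcome ties success to those objectives, and no sample size or primary estimate depends on subgroups. This stands as a limit on the consequence. It does not cancel a stated purpose that appears in both documents.

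A reader might infer that the plan will usually name a subgroup by chance. The documents do not support that. They give no naming rule, so the inference must supply one (the highest observed rate wins) and must also assume no true difference. Under a p ≤ 0.05 rule, chance naming would be at most about 3% per factor in the cases computed. Under a 25-point threshold, it is below half for one factor throughout the table. If a large true difference exists, the observed leader is usually the right one.

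A reader might also infer that no precision is planned. That is wrong, because within-group 95% intervals are already promised. What is missing is an interval for the difference.

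Finally, the sentence in the rationale is framed as a belief and can be read as describing the add-on population itself. It is not an analysis instruction.

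**Conclusion.** The point holds as a mismatch between a stated aim and the design. About 16 completers in a single uncontrolled arm cannot identify the population that benefits most from apremilast.

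The argument from the missing control rests on no numerical assumption. The argument from size rests on assumed rates and splits: a numerical leader with no true difference in 65% to 98% of trials for one factor, and 12% power for a 30-point difference at 8 versus 8. The 25-point figures move with the assumptions, from 9% to 48%, and should be quoted only as that range.

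The change is worth making before results are reported. The primary endpoint is unaffected.

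**What to change.** In the protocol's general statistical methods and in the SAP, replace the clause with wording such as:

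> Subgroup summaries by gender and by baseline treatment regimen (closed list) are exploratory. For each, report n, responders, an exact 95% CI, and the between-subgroup difference with a 95% CI. No subgroup will be described as the population that benefits most from apremilast.

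This keeps both planned factors as the documents name them. Aligning the sentence in the background and rationale is optional.

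The cost is a wording change in two documents, one extra interval per factor and a less ambitious stated aim. No additional subjects, visits or data are needed.

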PALACE 1, PALACE 2, and PALACE 3: The efficacy and safety of apremilast for the treatment of psoriatic arthritis was evaluated in 3 multi-center, randomized, double blind, placebo controlled studies of similar design. A total of 1493 adult patients with active psoriatic arthritis (PsA) (\geq 3 swollen joints and \geq 3 tender joints) despite prior or current treatment with disease-modifying antirheumatic drug (DMARD) therapy were randomized to placebo (n=496), apremilast 20 mg (n=500), or apremilast 30 mg (n-497) given orally twice daily. Patients were allowed to receive concurrent DMARD therapy. The primary endpoint, the percentage of patients achieving American College of Rheumatology (ACR) 20 response at week 16, was achieved by 38%, 32% and 41% of patients taking apremilast 30 mg twice daily +/- DMARDs in PsA-1, PsA-2, and PsA-3, respectively, with only 18-19% of patients on placebo +/- DMARDs resulted in greater improvement in psoriatic arthritis symptoms and was associated with a favorable safety profile. The most common adverse reactions leading to discontinuation for patients taking OTEZLA were nausea (1.8%), diarrhea (1.8%), and headache (1.2%).⁷

A Pilot Study of an Oral Phosphodiesterase Inhibitor (Apremilast) for Atopic Dermatitis in Adults): this open-label study tested the effects of apremilast 20 mg BID (APR20) and apremilast 30 mg BID (APR 30) in sixteen adults with atopic dermatitis. After three months, the group receiving APR20 had significant reductions in pruritus and the Dermatology Life Quality Index (DLQI), but not in the Eczema Area and Severity Index (EASI). The APR30 group had significant reductions in the EASI and DLQI.⁴

A. Objectives:

Efficacy Endpoints:

- a. Primary Endpoint Measures:
 - i. Proportion of patients who achieve an Investigator's Global Assessment (IGA) score of 0 (clear) or 1 (almost clear) at Week 16. Clinical improvement in a patient's eczematous lesions corresponds with a decrease in IGA, and a score of 0 (clear) or 1 (almost clear) is considered a significant clinical response.
- b. Secondary Outcome Measures
 - i. Proportion/percentage of subjects achieving BSA < 3%
 - ii. Mean and percentage change from baseline in percent of BSA involvement
 - iii. Mean and percent change of the Dermatology Life Quality Index (DLQI) from baseline
 - iv. Mean and percentage change from baseline in itch on Numerical Rating Scale (NRS) pruritus scale

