Study personnel will review the instructions printed on the package insert with subjects prior to dispensing the study medication. New study medication will be dispensed according to the Schedule of Assessments. The subject will be instructed to return the study medication packaging, including any unused medication, to the study site at each visit for assessment of compliance. Subjects will be asked whether they have taken their medication as instructed at each study visit. Any problems with compliance will be reviewed with the subject.

Compliance will be assessed in two ways. Subjects will be responsible for returning unused study drug to the site. Pills will be counted to determine compliance. Subjects will also be responsible for recording the date and time they take the study drug in a medication diary. Compliance is defined as taking between 75%-125% of dispensed study medication.

Dupilumab injections will also be recorded in the medication diary.

Withdrawal/Termination criteria:

The following are considered sufficient reasons for discontinuing a subject from study drug:

- Adverse events that the investigator believes may cause severe or permanent harm or which rule out continuation of study drug
- Lack of therapeutic effect:
 - Subjects who experience a significant flare of atopic dermatitis, as defined by a sudden intensification of eczema, or as a diagnosis of erythrodermic atopic dermatitis may be discontinued from treatment and enter the observational follow- up phase of the study.
 - In addition, if the subject, in his or her opinion, feels that their disease is worsening or not responding to treatment, they may withdraw consent to participate.
- Subject withdraws consent
- Subject lost to follow-up
- Death
- Protocol violation

The reason for discontinuation will be recorded in the subject's medical records.

D. Risk/benefit assessment:

- 1. **Physical risk**: Physical risk includes potential side effects or unknown adverse events related to study medication. It is unknown how the combination of apremilast with dupilumab will affect subjects. Side effects may be worse or intensified on this combination. Subjects may be at a slightly higher risk of infection than those taking the drugs individually, but this is unknown. It is unknown if this combination will improve atopic dermatitis. AD could stay the same or get worse.

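### The Week 16 IGA 0/1 rate is computed only in subjects who complete 16 weeks of treatment, so it likely overstates response among all subjects treated

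*Protocol*

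**What the plan says.** The primary endpoint in the protocol's Objectives is the "Proportion of patients who achieve an Investigator's Global Assessment (IGA) score of 0 (clear) or 1 (almost clear) at Week 16", with no restriction to completers. The analysis set comes from section II.B (General statistical methods), and the SAP repeats it word for word: "Efficacy analyses will only use data from participants who complete at least 16 weeks of study treatment in order to evaluate the primary endpoint".

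Section II.B expects losses but gives no rate: "A rate of incompletion and/or drop out of subjects has been factored in to assure great than 16 patients will complete the study". The Sample size paragraph plans up to 20 screened and 16 completing. The Recruitment paragraph (section G) adds that the 20 must also cover screen failures.

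The Withdrawal/Termination criteria list adverse events and lack of therapeutic effect as reasons to stop. Lack of effect covers "Subjects who experience a significant flare of atopic dermatitis, as defined by a sudden intensification of eczema", and also a subject's own view that the disease is worsening or not responding.

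Two sentences under Secondary Endpoints bear on missing data: "Assessment of outcomes of each protocol-scheduled time point (Weeks 2, 4, 8, 16, and 24) will be performed for each endpoint" and "Various schemes will be assessed for missing data imputation if needed". Neither appears in the SAP. The safety analysis uses everyone who takes at least one dose. The Schedule of Assessments includes IGA, BSA, EASI, NRS and DLQI at the Early Termination visit.

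**The concern.** The efficacy set is defined by something that happens after treatment starts, and that event is linked to outcome by the protocol's own stopping reasons. The study asks whether adding apremilast moves inadequate dupilumab responders to IGA 0/1. A subject who stops at Week 8 because the eczema flared is a failure on that question, yet under the rule is not counted at all. There is no control arm in which similar selection might offset this.

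The imputation sentence does not settle the matter. If it is meant for early stoppers, it conflicts with the completer rule. If it covers only visits missed by completers, early stoppers remain excluded. Either way, no method is named, which leaves the choice open in an unblinded study.

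Read literally, the rule also removes the Week 2, 4 and 8 values of anyone who stops before Week 16, although an assessment at each visit is planned.

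At stake is the headline number: a response rate among those who stayed on treatment could be read as the response rate of those treated.

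**Working it through.** **What the plan's figures allow.** There is no power calculation, target rate or numeric drop-out rate to reproduce. Screening 20 to have 16 complete allows a total loss of (20 − 16)/20 = 20%, shared between screen failure and drop-out. The number dosed is therefore an assumption below.

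**Formulas.** Let *c* be the subjects completing 16 weeks and *n* the subjects dosed.

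- No early stopper responds: relative excess of the completer rate over the all-dosed rate = *n*/*c* − 1.
- Early stoppers respond at half the completer rate: excess = *n*/(*c* + (*n* − *c*)/2) − 1.
- Early stoppers respond at the completer rate: excess = 0.

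**Relative excess with c = 16**

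| Dosed (n) | No stopper responds | Half the completer rate |
|---|---|---|
| 17 | 17/16 − 1 = 6.25% | 17/16.5 − 1 = 3.0% |
| 18 | 18/16 − 1 = 12.5% | 18/17 − 1 = 5.9% |
| 19 | 19/16 − 1 = 18.75% | 19/17.5 − 1 = 8.6% |
| 20 (no screen failures) | 20/16 − 1 = 25% | 20/18 − 1 = 11.1% |

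**Example with 8 responders, all among completers (Clopper-Pearson 95% intervals)**

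| Denominator | Rate | 95% CI | Shift from completers |
|---|---|---|---|
| 16 (completers) | 50.0% | 24.7–75.3 | – |
| 17 dosed | 47.1% | 23.0–72.2 | 2.9 points |
| 18 dosed | 44.4% | 21.5–69.2 | 5.6 points |
| 20 dosed | 40.0% | 19.1–63.9 | 10.0 points |

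**Other numbers of completers, 20 dosed, no stopper responding**

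- *c* = 14: 20/14 − 1 = 43% (20/17 − 1 = 18% at half response). For example, 7/14 = 50.0% (23.0–77.0) against 7/20 = 35.0% (15.4–59.2).
- *c* = 17: 20/17 − 1 = 18%.
- *c* = 18: 20/18 − 1 = 11%.

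The last two matter because the planned 16 refers to completing a 24-week study, so more than 16 may reach Week 16.

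**Direction.** If 16 complete, 8 of them respond, and all 4 early stoppers out of 20 also respond, the all-dosed rate is 12/20 = 60%, above the completer 50%. Upward bias is therefore the likely direction, not a certain one. It requires early stoppers to respond less often than completers.

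**How many might stop.** The only discontinuation figures in the documents are in section 2.2.1, for psoriatic arthritis: 1.8%, 1.8% and 1.2% for the commonest adverse reactions. If they do not overlap they sum to 4.8%, which is 0.048 × 17 = 0.82 to 0.048 × 20 = 0.96 subjects, or about one. They come from another disease, cover three reactions only, and leave out lack of effect.

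**The case against.** The strongest reply is that the plan is open about what it does. The analysis set is stated just before the endpoint is restated, so a careful reader knows that the result is a completer proportion. The analysis is descriptive ("The analysis will be primarily descriptive"), with no null rate, test or threshold. With about one early stop, the shift is 2.9 points against an interval roughly 50 points wide. The 25% figure needs every screened subject to be dosed, and the 43% figure assumes fewer completers than planned. Responder counts and a drop-out table are planned, so a reader could largely rebuild the all-dosed rate. All of this stands, and it limits the seriousness of the point. It does not change what the reported proportion and its interval would describe.

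The imputation sentence can be read as covering only completers with a missed visit, in which case nothing conflicts. That is a fair reading, but early stoppers then stay out and the method is still unnamed.

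The rule's closing words on evaluating the primary endpoint may limit it to that purpose, so loss of the early-visit data is not certain. The primary result would be completers-only on either reading.

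Finally, counting every early stop as failure is conservative. Some stops need not track outcome, such as death, loss to follow-up, protocol violation, or the discontinuation the protocol requires on pregnancy. This is a real cost of the remedy and a reason to keep the completer analysis beside it.

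**Conclusion.** The concern holds. The primary result as planned describes subjects who stayed on treatment for 16 weeks, and the protocol's own stopping reasons make it likely to be too high for the treated group. With 16 completers, the relative excess runs from 6% (17 dosed) to 25% (20 dosed) if no early stopper responds, and from 3% to 11% if they respond at half the completer rate. It is zero if nobody stops before Week 16 or if stoppers respond equally. These are scenarios, not bounds: numbers dosed, drop-out and response rates are all assumed. The same factors apply to the BSA < 3% endpoint. Bias in mean changes cannot be sized from the documents.

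The shift sits inside wide intervals and no decision rule depends on it, but it is systematic and inexpensive to remove. It should be fixed. Confidence is high about the rule and its effect on the denominator; the size remains unknown.

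**What to change.** Replace the completer sentence in both the protocol and the SAP with:

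> The primary efficacy analysis includes all subjects who take at least one dose of study medication. Subjects who stop study drug before the Week 16 visit, or who have no Week 16 IGA, are counted as non-responders, and the proportion is reported with its exact 95% confidence interval. The same rule applies to BSA < 3%. The analysis of subjects who complete 16 weeks is a sensitivity analysis.

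Replace the imputation sentence in the protocol, and add to the SAP:

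> Continuous endpoints are summarised for all dosed subjects at each visit, with the number contributing. A sensitivity summary uses the last available value, including the Early Termination assessment. Mean changes at Week 16 remain subject to drop-out.

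The cost is wording only. The all-dosed set already exists for safety, and the Early Termination assessments are already scheduled. The response rate may come out somewhat lower, stops unrelated to outcome are counted conservatively, and the primary result does not use the Early Termination IGA. Carrying the last value forward rests on its own assumption, which is why it is only a sensitivity summary.
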